APPENDIX D: SYMPTOM AND PAIN BASELINE ASSESSMENT

Confidential

Phase II SBRT Spine Protocol
Page 1 of 4Dual Enrolled Sbrt Mdasigi Pain Assessment Baseline
(version AB)

Name (Last, First) _____

0 (not present)	1	2	3	4	5	6	7	8	9	10 (as bad as you can imagine)
-----------------	---	---	---	---	---	---	---	---	---	--------------------------------

Fatigue (tiredness) at its WORST in the last 24 hours?

Feeling drowsy (sleepy) at its WORST in the last 24 hours?

Disturbed sleep at its WORST in the last 24 hours?

Problem with remembering things at its WORST in the last 24 hours?

Feeling sad at its WORST in the last 24 hours?

Feelings of being distressed (upset) at its WORST in the last 24 hours?

0 (not present)	1	2	3	4	5	6	7	8	9	10 (as bad as you can imagine)
-----------------	---	---	---	---	---	---	---	---	---	--------------------------------

Shortness of breath at its WORST in the last 24 hours?

Having a dry mouth at its WORST in the last 24 hours?

Nausea at its WORST in the last 24 hours?

Vomiting at its WORST in the last 24 hours?

Problem with lack of appetite at its WORST in the last 24 hours?

0 (not present)	1	2	3	4	5	6	7	8	9	10 (as bad as you can imagine)
-----------------	---	---	---	---	---	---	---	---	---	--------------------------------

Confidential

Page 2 of 4

Difficulty swallowing at its WORST in the last 24 hours?											
Pain with swallowing at its WORST in the last 24 hours?											
Acid, indigestion, or heartburn at its WORST in the last 24 hours?											
Diarrhea or loose stools at its WORST in the last 24 hours?											
Change in bowel pattern (diarrhea/constipation) at its WORST in the last 24 hours?											
Loss of control of bowel and/or bladder at its WORST in the last 24 hours?											
	0 (not present)	1	2	3	4	5	6	7	8	9	10 (as bad as you can imagine)

Numbness or tingling at its WORST in the last 24 hours?											
Radiating spine pain (starting in one place and going to another) at its WORST in the last 24 hours?											
Weakness in the arms and/or legs at its WORST in the last 24 hours?											
Sexual function at its WORST in the last 24 hours?											

Confidential

Page 3 of 4

How have your symptoms interfered with your life? Symptoms frequently interfere with how we feel and function. How much have your symptoms interfered with the following items in the last 7 days from 0 (did not interfere) to 10 (interfered completely):

	0 (did not interfere)	1	2	3	4	5	6	7	8	9	10 (interfered completely)
General Activity in the last 24 hours?											
Mood in the last 24 hours?											
Work (including work around the house) in the last 24 hours?											
Relations with other people in the last 24 hours?											
Walking in the last 24 hours?											
Enjoyment for life in the last 24 hours?											

Pain Assessment

Please rate your pain at its WORST in the last 24 hours on a scale of 0-10 with 0 being no pain at all, 10 being worst pain imaginable
(Includes pain related and unrelated to cancer)

0 1 2 3 4 5 6 7 8 9 10

Location of maximum pain _____

Location of first site receiving radiation (to be filled in by study staff) _____

Please rate your maximum pain in the past 24 hours at this treatment site (site 1, specified above) where you will be receiving radiation therapy.

0 (no pain), 10 (as bad as you can imagine)

0 1 2 3 4 5 6 7 8 9 10

Location of second site receiving radiation (to be filled in by study staff) _____

Confidential

Page 4 of 4

Please rate your maximum pain in the past 24 hours at this treatment site (site 2, specified above) where you will be receiving radiation therapy.

0 (no pain), 10 (as bad as you can imagine)

0 1 2 3 4 5 6 7 8 9 10

Location of third site receiving radiation (to be filled in by study staff) _____

Please rate your maximum pain in the past 24 hours at this treatment site (site 3, specified above) where you will be receiving radiation therapy.

0 (no pain), 10 (as bad as you can imagine)

0 1 2 3 4 5 6 7 8 9 10

Medication Review

Have you taken any medications for pain in the last 7 days?

Yes
 No

What kinds of pain medications are you taking? Check all that apply. If you are unsure, please ask your provider before answering this question.

Narcotic pain medications (ex. morphine, oxycodone, dilaudid, or similar medications)
 Non-narcotic pain medications (ex. tylenol, ibuprofen, etc)

Have you taken any medications for HEARTBURN or REFLUX in the last 7 days?

Yes
 No
(Examples include (but not limited to): zofran or ondansetron, compazine or prochlorperazine, reglan or metoclopramide, ativan)

Have you taken any medications for NAUSEA in the last 7 days?

Yes
 No
(Examples include (but not limited to): Prilosec or omeprazole, Protonix or pantoprazole, Nexium or esomeprazole, Zantac or ranitidine)

Have you taken any medications for DIARRHEA in the last 7 days?

Yes
 No
(Examples include (but not limited to): imodium, lomotil)

APPENDIX E: SYMPTOM AND PAIN ASSESSMENT IN THE PAST 24 HOURS

Confidential

Phase II SBRT Spine Protocol

Page 1 of 5

**Dual Enrolled Sbrt Mdasigi Pain Assessment Followup
(version D)**

Name (Last, First)

0 (not present)	1	2	3	4	5	6	7	8	9	10 (as bad as you can imagine)
-----------------	---	---	---	---	---	---	---	---	---	--------------------------------

Fatigue (tiredness) at its WORST in the last 24 hours? Feeling drowsy (sleepy) at its WORST in the last 24 hours? Disturbed sleep at its WORST in the last 24 hours? Problem with remembering things at its WORST in the last 24 hours? Feeling sad at its WORST in the last 24 hours? Feelings of being distressed (upset) at its WORST in the last 24 hours?

0 (not present)	1	2	3	4	5	6	7	8	9	10 (as bad as you can imagine)
-----------------	---	---	---	---	---	---	---	---	---	--------------------------------

Shortness of breath at its WORST in the last 24 hours? Having a dry mouth at its WORST in the last 24 hours? Nausea at its WORST in the last 24 hours? Vomiting at its WORST in the last 24 hours? Problem with lack of appetite at its WORST in the last 24 hours?

0 (not present)	1	2	3	4	5	6	7	8	9	10 (as bad as you can imagine)
-----------------	---	---	---	---	---	---	---	---	---	--------------------------------

Confidential

Page 2 of 5

Difficulty swallowing at its WORST in the last 24 hours?											
Pain with swallowing at its WORST in the last 24 hours?											
Acid, indigestion, or heartburn at its WORST in the last 24 hours?											
Diarrhea or loose stools at its WORST in the last 24 hours?											
Change in bowel pattern (diarrhea/constipation) at its WORST in the last 24 hours?											
Loss of control of bowel and/or bladder at its WORST in the last 24 hours?											
	0 (not present)	1	2	3	4	5	6	7	8	9	10 (as bad as you can imagine)

Numbness or tingling at its WORST in the last 24 hours?											
Weakness in the arms and/or legs at its WORST in the last 24 hours?											
Radiating spine pain (starting in one place and going to another) at its WORST in the last 24 hours?											
Sexual function at its WORST in the last 24 hours?											

Confidential

Page 3 of 5

How have your symptoms interfered with your life? Symptoms frequently interfere with how we feel and function. How much have your symptoms interfered with the following items in the last 24 HOURS from 0 (did not interfere) to 10 (interfered completely):

	0 (did not interfere)	1	2	3	4	5	6	7	8	9	10 (interfered completely)
General Activity in the last 24 hours?											
Mood in the last 24 hours?											
Work (including work around the house) in the last 24 hours?											
Relations with other people in the last 24 hours?											
Walking in the last 24 hours?											
Enjoyment for life in the last 24 hours?											

Pain Assessment

Please rate your pain at its WORST in the last 24 hours on a scale of 0-10 with 0 being no pain at all, 10 being worst pain imaginable
(Includes pain related and unrelated to cancer)

0 1 2 3 4 5 6 7 8 9 10

Location of maximum pain _____

Location of first site receiving radiation (to be filled in by study staff) _____

Please rate your maximum pain in the past 24 hours at this treatment site (site 1, specified above) where you have received radiation therapy.

0 (no pain), 10 (as bad as you can imagine)

0 1 2 3 4 5 6 7 8 9 10

Confidential

Page 4 of 5

Please estimate the percent improvement in pain you have experienced at this treatment site (site 1, specified above) since starting radiation therapy.

0% (no change in pain or pain has worsened) to 100% (pain completely resolved)

0% 10% 20% 30% 40% 50% 60% 70% 80% 90%
 100%

Location of second site receiving radiation (to be filled in by study staff) _____

Please rate your maximum pain in the past 24 hours at this treatment site (site 2, specified above) where you have received radiation therapy.

0 (no pain), 10 (as bad as you can imagine)

0 1 2 3 4 5 6 7 8 9 10

Please estimate the percent improvement in pain you have experienced at this treatment site (site 2, specified above) since starting radiation therapy.

0% (no change in pain or pain has worsened) to 100% (pain completely resolved)

0% 10% 20% 30% 40% 50% 60% 70% 80% 90%
 100%

Location of third site receiving radiation (to be filled in by study staff) _____

Please rate your maximum pain in the past 24 hours at this treatment site (site 3, specified above) where you have received radiation therapy.

0 (no pain), 10 (as bad as you can imagine)

0 1 2 3 4 5 6 7 8 9 10

Please estimate the percent improvement in pain you have experienced at this treatment site (site 3, specified above) since starting radiation therapy.

0% (no change in pain or pain has worsened) to 100% (pain completely resolved)

0% 10% 20% 30% 40% 50% 60% 70% 80% 90%
 100%

Medication review

Have you started or increased your dose of any medications since last follow-up (or since starting radiation if this is your first follow-up) because you have experienced DIARRHEA?

Yes
 No
 (Examples include (but not limited to): imodium, lomotil)

Have you started or increased your dose of any medications since last follow-up (or since starting radiation if this is your first follow-up) because you have experienced NAUSEA?

Yes
 No
 (Examples include (but not limited to): zofran or ondansetron, compazine or prochlorperazine, reglan or metoclopramide, ativan)

Confidential

Page 5 of 5

Have you started or increased your dose of any medications since last follow-up (or since starting radiation if this is your first follow-up) because you have experienced HEARTBURN?

Yes

No

(Examples include (but not limited to): Prilosec or omeprazole, Protonix or pantoprazole, Nexium or esomeprazole, Zantac or ranitidine)

Have you started or increased your dose of any medications since last follow-up (or since starting radiation if this is your first follow-up) because you have experienced SORE THROAT?

Yes

No

Which medications have you started or increased in dose? Check all that apply:

- magic mouth wash
- narcotic pain medications (i.e. morphine, oxycodone, dilaudid, or similar)
- non-narcotic pain medications
- other

If other, please describe

APPENDIX F: PAIN AND SYMPTOM ASSESSMENT IN THE PAST 7 DAYS (FOLLOW-UP)
Confidential

Phase II SBRT Spine Protocol
 Page 1 of 6

**Dual Enrolled SbRT Mdasigi Pain Assessment 1wk 4wk
 (version CE)**

Name (Last, First) _____

	0 (not present)	1	2	3	4	5	6	7	8	9	10 (as bad as you can imagine)
Fatigue (tiredness) at its WORST in the last 24 hours?											
...in the last 7 days?											
Feeling drowsy (sleepy) at its WORST in the last 24 hours?											
...in the last 7 days?											
Disturbed sleep at its WORST in the last 24 hours?											
...in the last 7 days?											
Problem with remembering things at its WORST in the last 24 hours?											
...in the last 7 days?											
Feeling sad at its WORST in the last 24 hours?											
...in the last 7 days?											
Feelings of being distressed (upset) at its WORST in the last 24 hours?											
...in the last 7 days?											
	0 (not present)	1	2	3	4	5	6	7	8	9	10 (as bad as you can imagine)

Confidential

Page 2 of 6

Shortness of breath at its WORST in the last 24 hours?											
...in the last 7 days?											
Dry mouth at its WORST in the last 24 hours?											
...in the last 7 days?											
	0 (not present)	1	2	3	4	5	6	7	8	9	10 (as bad as you can imagine)

Nausea at its WORST in the last 24 hours?											
...in the last 7 days?											
Vomiting at its WORST in the last 24 hours?											
...in the last 7 days?											
Lack of appetite at its WORST in the last 24 hours?											
...in the last 7 days?											
	0 (not present)	1	2	3	4	5	6	7	8	9	10 (as bad as you can imagine)

Difficulty swallowing at its WORST in the last 24 hours?											
...in the last 7 days?											
Pain with swallowing at its WORST in the last 24 hours?											
...in the last 7 days?											
Acid, indigestion, or heartburn at its WORST in the last 24 hours?											
...in the last 7 days?											

Confidential

	0 (not present)	1	2	3	4	5	6	7	8	9	Page 3 of 6 10 (as bad as you can imagine)
Diarrhea or loose stools at its WORST in the last 24 hours?											
...in the last 7 days?											
Change in bowel pattern (diarrhea/constipation) at its WORST in the last 24 hours?											
...in the last 7 days?											
Loss of control of bowel and/or bladder at its WORST in the last 24 hours?											
...in the last 7 days?											
	0 (not present)	1	2	3	4	5	6	7	8	9	10 (as bad as you can imagine)
Numbness or tingling at its WORST in the last 24 hours?											
...in the last 7 days?											
Weakness in the arms and/or legs at its WORST in the last 24 hours?											
...in the last 7 days?											

Confidential

	0 (not present)	1	2	3	4	5	6	7	8	9	10 (as bad as you can imagine)
Radiating spine pain (starting in one place and going to another) at its WORST in the last 24 hours?											
...in the last 7 days?											
Your sexual function at its WORST in the last 24 hours?											
...in the last 7 days?											

Part II. How have your symptoms interfered with your life?

Symptoms frequently interfere with how we feel and function. How much have your symptoms interfered with the following items in the last 24 HOURS and LAST 7 DAYS from 0 (did not interfere) to 10 (interfered completely):

	0 (did not interfere)	1	2	3	4	5	6	7	8	9	10 (interfered completely)
General Activity in the last 24 hours?											
...in the last 7 days?											
Mood in the last 24 hours?											
...in the last 7 days?											
Work (including work around the house) in the last 24 hours?											
...in the last 7 days?											

Confidential

	0 (did not interfere)	1	2	3	4	5	6	7	8	9	10 (interfered completely)
Relations with other people in the last 24 hours?											
...in the last 7 days?											
Walking in the last 24 hours?											
...in the last 7 days?											
Enjoyment for life in the last 24 hours?											
...in the last 7 days?											

Part III. Pain Assessment

Please rate your pain at its WORST in the last 24 hours.

0 (no pain), 10 (as bad as you can imagine)
(Includes pain related and unrelated to cancer) 0 1 2 3 4 5 6 7 8 9 10

Location of maximum pain _____

Location of first site receiving radiation (to be filled in by study staff) _____

Please rate your maximum pain in the past 24 hours at this first treatment site (specified above) where you have received radiation therapy.

0 (no pain), 10 (as bad as you can imagine)

 0 1 2 3 4 5 6 7 8 9 10

Please estimate the percent improvement in pain you have experienced at this first treatment site (specified above) since starting radiation therapy.

0% (no change in pain or pain has worsened) to 100% (pain completely resolved)

 0% 10% 20% 30% 40% 50% 60% 70% 80% 90%
 100%

Location of second site receiving radiation (to be filled in by study staff) _____

Confidential

Page 6 of 6

Please rate your maximum pain in the past 24 hours at this second treatment site (specified above) where you have received radiation therapy.

0 (no pain), 10 (as bad as you can imagine)

0 1 2 3 4 5 6 7 8 9 10

Please estimate the percent improvement in pain you have experienced at this second treatment site (specified above) since starting radiation therapy.

0% (no change in pain or pain has worsened) to 100% (pain completely resolved)

0% 10% 20% 30% 40% 50% 60% 70% 80% 90%
 100%

Location of third site receiving radiation (to be filled in by study staff) _____

Please rate your maximum pain in the past 24 hours at this third treatment site (specified above) where you have received radiation therapy.

0 (no pain), 10 (as bad as you can imagine)

0 1 2 3 4 5 6 7 8 9 10

Please estimate the percent improvement in pain you have experienced at this third treatment site (specified above) since starting radiation therapy.

0% (no change in pain or pain has worsened) to 100% (pain completely resolved)

0% 10% 20% 30% 40% 50% 60% 70% 80% 90%
 100%

Part IV. Medication review

Have you started or increased your dose of any medications since last follow-up because you have experienced DIARRHEA?

Yes
 No

Have you started or increased your dose of any medications since last follow-up because you have experienced NAUSEA?

Yes
 No

Have you started or increased your dose of any medications since last follow-up because you have experienced HEARTBURN?

Yes
 No

Have you started or increased your dose of any medications since last follow-up because you have experienced SORE THROAT?

Yes
 No

Which medications have you started or increased in dose? Check all that apply:

magic mouth wash
 narcotic pain medications (i.e. morphine, oxycodone, dilaudid, or similar)
 non-narcotic pain medications
 other

If other, please describe _____

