11.2.5 Timing of Assessments

Baseline assessments will be done for the target lesion, non-target lesion(s), pre-existing toxicity and QOL. Participants' first assessment post-treatment will occur at 1 week (\pm 3 days) to assess for QOL. Participants will then undergo another evaluation at 1 month (\pm 1

week) to assess for QOL. Participants will then be evaluated at 3 months (\pm 4 weeks) with imaging (CT or MRI as per treating physician) done at the time of follow-up (\pm 2 weeks). Participants will then be evaluated at 6 months (\pm 2 months) and every 6 months thereafter through year 2 (\pm 3 months) and annually years 3-5 (\pm 6 months), with imaging (CT or MRI as per treating physician) done at the time of follow-up (\pm 2 weeks). We will attempt to coordinate all visits and scans with the patient's other medical providers to avoid duplicate visits or scans and minimize inconvenience to the patient and protocol violations. Please see Appendix B for additional study parameters.

	Pre-Study	Treatment	Week 1 ^b	Month 1 ^c	Month 3 ^d	Month 6 ^e	Every 6 months after month 6 through year 2 ^f	Annually Years 3-5 ^g
Target Lesion(s)	X				X	X	X	X
Toxicity Assessment	X	X ^h			X	X	X	X
QOL Assessment	X	X ^a	X	X	X	X	X	X

a: On mid-point and last day of radiation

b: \pm 3 days

c: \pm 1 week

d: \pm 4 weeks

e: \pm 2 months

f: \pm 3 months

g: \pm 6 months

h: During on treatment visit

Note: The baseline “pre-study” questionnaire can be given anytime between the initial consult appointment and the first radiation therapy treatment, as long as the patient has not yet received radiation

Note: Imaging will be done at clinicians' discretion.

Participants will be given the option on each survey to decline.

Administration of questionnaires will be determined, as follows, by the time of follow-up.

Questionnaire Version	Timeline	Appendix Reference
Symptom and Pain Baseline Assessment	Prior to initial RT	Appendix D
Symptom and Pain Assessment in the Past 24 Hours	Mid-point and on last day of treatment	Appendix E
Symptom and Pain Assessment in the Past 7 Days	1 week and 4 week follow-up	Appendix F
Symptom and Pain Assessment, Long-Term Follow-Up	3 months, every 6 months for 2 years, and annually from years 3 to 5	Appendix G

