APPENDIX B STUDY PARAMETERS

Assessments	Pre-Study	Simulation	Radiation Treatment	Follow-Up ⁽¹⁾
Informed Consent and Registration	X			
History/physical/vital signs	X			X
Performance Status	X			X
Pregnancy Test (B-HCG)	X			
Diagnostic CT or MRI (at discretion of treating physician)		X ⁽²⁾		
Imaging study (CT or MRI to be determined by treating physician)				X ⁽³⁾
Toxicity Assessment	X		X ⁽⁶⁾	X
QOL questionnaire	X		X ⁽⁴⁾	X ⁽⁵⁾

- (1) Follow up schedule: initial evaluation at 1 week after completion of radiation therapy (via telephone, in person or email), then at 1 month after completion (via telephone, in person or email), 3 months, 6 months and every 6 months thereafter through year 2 (in person, telephone or email), then annually through year 5. Visits can be scheduled within a pre-specified time window around the anticipated date.
- (2) Baseline imaging is to be done within 21 days of start of first fraction of radiation
- (3) Follow up imaging is to be done within 2 weeks before or after scheduled follow up visit.
- (4) On mid-point and last day of radiation
- (5) QOL questionnaire to be completed within 2 weeks of follow up visit.
- (6) During on treatment visit

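### On the week-1 and week-4 form (Appendix F), worst pain and treated-site pain have only 24-hour recall, so a short pain flare can leave no patient-reported pain rating.

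*Combined protocol and SAP*

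**What the plan says.** The questionnaire table in section 11.2.5 names the form "Symptom and Pain Assessment in the Past 7 Days" and assigns it to the "1 week and 4 week follow-up". The Appendix F heading gives the same recall period.

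The form itself is built as follows.

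- **Part I** has 21 symptom rows and **Part II** has 6 interference rows. Each has a 24-hour line followed by a 7-day line. One symptom row is "Radiating spine pain (starting in one place and going to another) at its WORST in the last 24 hours", also with a 7-day line beneath it.
- **Part III** opens with "Please rate your pain at its WORST in the last 24 hours" and then, for each of up to three treated sites, asks for the maximum: "Please rate your maximum pain in the past 24 hours at this first treatment site (specified above) where you have received radiation therapy". None of these four ratings has a 7-day line.
- **Part III** also asks for percent improvement at each treated site since radiation began, on a scale anchored "0% (no change in pain or pain has worsened) to 100% (pain completely resolved".
- **Part IV** asks about new or increased medication for diarrhea, nausea, heartburn and sore throat.

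On timing, section 11.2.5 sets the week-1 contact at ±3 days and the month-1 contact at ±1 week. Appendix B, footnote 5, says: "QOL questionnaire to be completed within 2 weeks of follow up visit".

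**The concern.** Pain is the first symptom in the Appendix F title, yet its ratings lack the recall period that the title promises, and no reason is given. Pain flare is the acute pain event the protocol itself expects: section 6.9.2 lists it as common, section 1.2 reports it among the most frequent toxicities in a cited non-spine series, and section 9 gives it as the purpose of optional dexamethasone. Symptom control and acute toxicity are secondary objectives (section 2.3).

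If a flare has settled by the day before the form, the patient has nowhere to rate it at the treated site. Acute pain after SBRT could then look milder in the patient-reported data than it was.

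**Working it through.** The plan states no figure for flare detection, so there is none to reproduce. The check has three parts.

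**1. Does anything else on the form fill the gap?**

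- Radiating spine pain and pain with swallowing have 7-day lines, but neither rates pain at the treated site.
- Percent improvement looks back far enough, but places no change and worsening together at 0%, so it cannot show a flare.
- Part IV does not ask about medication started for pain. Its list of drugs includes narcotics, but it follows four questions on other symptoms.
- Appendix E, completed on the last treatment day, also has 24-hour recall. After a single fraction with the next form on day 7, treated-site pain is unrated from the end of treatment to day 6.

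**2. How much could be missed?** The documents give neither onset nor duration for pain flare, so both are assumptions. Take a single-fraction patient (18 Gy x 1 is one of the section 6.1.1 regimens), onset s uniform over days 0 to 5, duration d days, and the form on day 7. The 24-hour window is days 6 to 7. A flare overlaps it if s + d > 6, that is s > 6 − d. Hence

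P(overlap) = [5 − (6 − d)] / 5 = (d − 1) / 5, for d from 1 to 6.

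| Duration (days) | 24-hour recall | 7-day recall |
|---|---|---|
| 1 | 0/5 = 0% | 100% |
| 2 | 1/5 = 20% | 100% |
| 3 | 2/5 = 40% | 100% |
| 5 | 4/5 = 80% | 100% |
| 6 or more | 5/5 = 100% | 100% |

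The 7-day column is 100% because that window covers days 0 to 7, which contain every assumed onset.

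Sensitivity to these assumptions:

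- Form spread evenly over days 4 to 10 (the ±3-day window), same onset: 24-hour recall overlaps 13%, 25%, 40% and 72% of flares of 1, 2, 3 and 5 days, and 92% at 7 days. Seven-day recall overlaps 92%, 97% and 98% at 1, 2 and 3 days.
- A day-by-day count using both forms (day 7 ± 3 and day 28 ± 7) and onset on days 0 to 6: 8%, 18%, 31% and 57% with 24-hour recall, against 76%, 82%, 86% and 88% with 7-day recall, for 1, 2, 3 and 5 days.
- The same count with onset spread over days 0 to 29: 6% against 41% for 1-day flares, and 30% against 57% for 5-day flares.

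**3. Do the schedules secure the other route?**

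- Section 11.2.5 gives week 1 and month 1 a QOL purpose, and its table marks no toxicity assessment there.
- The section 12.2 table has adverse-event evaluation within 1 week after completion and next at 4 months. Its 2-week and 5-week columns contain only the questionnaire.
- Appendix B marks toxicity assessment at follow-up, and its follow-up schedule includes week 1 and month 1.
- Appendix C has adverse events assessed at every evaluation time point, and follows to resolution those arising up to 30 days after the last intervention.

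These do not agree. The questionnaire window also conflicts: section 11.2.5 ends the week-1 window on day 7 + 3 = 10, whereas footnote 5 read against a day-7 visit allows day 7 + 14 = 21. A form on day 21 with 7-day recall would cover days 14 to 21 and miss the first week.

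**The case against.** The strongest reply is that toxicity is graded by CTCAE (section 11.2.3), not from this form, and that Appendices B and C provide adverse-event assessment at follow-up contacts. Treated-site pain is also checked in every patient at on-treatment visits (section 6.9.1). With 9 Gy x 3 or 6 Gy x 5, flares during the course can be caught there or on the mid-point and last-day forms. This stands in part: the form is not the only route, and the single-fraction case is the least favourable. But the on-treatment checks stop with treatment, and the schedules disagree on week 1 and month 1.

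Second, 24-hour pain recall is common to Appendices D, E, F and G, which supports comparison over time. A 7-day maximum set against a 24-hour baseline would be biased upward, and a form on day 4 would reach back about 3 days before a single fraction. Overlap of a recall window with a flare is also not the same as detecting one. All of this stands. It is a reason to keep the 24-hour lines and not to treat the 7-day lines as change from baseline; it is not a reason to omit them from a form titled for 7 days.

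Third, no named analysis uses these ratings at week 1. The primary endpoint is 6-month local control, and the main QOL test compares baseline with 3 months, using Appendices D and G. This stands and limits the importance of the point.

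**Conclusion.** The gap is real and limited. Overall worst pain and treated-site pain have 24-hour recall only on a form titled for 7 days, unlike all 27 other rated symptom and interference items (21 + 6). The patient-reported record can therefore miss a short flare that ended more than 24 hours before the form. Under the day-7 model the overlap runs from 0% for a 1-day flare to 100% at 6 days or more, resting on assumed onset and duration.

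A reader might infer more, in three ways that the documents do not support.

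- *That the form asks about pain only over 24 hours.* Radiating spine pain and pain with swallowing have 7-day lines, and percent improvement looks back to the start of radiation.
- *That most flares are missed.* This holds only if flares are short. Section 6.9.2 says only that short-term reactions as a class appear during treatment or within 1 month and generally resolve within 2-3 months. With a true flare rate of 20%, the rate overlapped by the form would be anywhere from 20% × 0 = 0% to 20% × 1 = 20% under the day-7 model.
- *That acute pain toxicity will be under-reported overall.* The adverse-event route may record it; whether it does at week 1 and month 1 depends on which schedule is followed.

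The effect is confined to secondary reporting of symptoms and acute toxicity.

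**What to change.** 1. In Appendix F Part III, add a 7-day line under overall worst pain and under the maximum-pain rating for each treated site, in the layout of Parts I and II. Keep the 24-hour lines for comparison with the 24-hour baseline ratings.
2. Reconcile Appendix B footnote 5 with the section 11.2.5 windows (±3 days at week 1, ±1 week at month 1). Without this, a late form could miss the first week even with 7-day recall.
3. Reconcile sections 11.2.5 and 12.2 with Appendices B and C on whether toxicity is assessed at week 1 and month 1.

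The cost is up to four extra lines on one form, an update to the REDCap form, and edits to the footnote and schedules. The questionnaire change needs no extra visit. The downsides are a slightly longer form, no 7-day ratings for patients already assessed, a 7-day maximum that is not directly comparable with the 24-hour baseline, and early forms whose recall may include pre-treatment days. The report should state these limits.
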